5.5.2 Key secondary analysis

The key secondary objectives:

- H_2 : secukinumab is not different to placebo regimen with respect to ACR 20 response at Week 12.
- H_3 : secukinumab s.c. is not different to placebo regimen with respect to ACR 50 response at Week 12.
- H_4 : secukinumab s.c. is not different to placebo regimen with respect to the change in SPARCC enthesitis index from Baseline to Week 12.

H_2 will be tested as follows:-

ACR 20 at Week 12 = Treatment + weight.

The procedure PROC LOGISTIC will be used to perform the logistic regression analysis. Treatment regimen will be set as a class variable. The model statement will be based on the formula outlined above. Reference coding will be used in the model. The odds ratios will be computed for comparison of secukinumab versus placebo using the logistic regression model fitted. If the initial model does not converge Firth's penalized maximum likelihood estimation method will be used.

H_3 will be analysed analogous to H_2 above.

H_4 will be analysed analogous to the primary efficacy variable.

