Response at Week 12 in ACR 20 in the FAS will be evaluated using a logistic regression model with study treatment as a factor and baseline weight as a covariate. The odds ratios will be computed for comparison of secukinumab versus placebo using the logistic regression model fitted. In cases where separation is a concern for secondary endpoint at Week 12 an exact logistic regression model will be applied to all visits. To ensure convergence, this model will not include any continuous covariates. When exact logistic regression is unable to be implemented then Fisher's exact test will be applied. In this case no odds ratios or confidence intervals can be estimated but p-values may be calculated.

ACR 50 at Week 12

Response at Week 12 in ACR 50 in the FAS will be evaluated using a logistic regression model with study treatment as a factor and baseline weight as a covariate. The odds ratios will be computed for comparison of secukinumab versus placebo using the logistic regression model fitted. In cases where separation is a concern for secondary endpoint at Week 12 an exact logistic regression model will be applied to all visits. To ensure convergence, this model will not include any continuous covariates. When exact logistic regression is unable to be implemented then Fisher's exact test will be applied. In this case no odds ratios or confidence intervals can be estimated but p-values may be calculated.

Changes in SPARCC at Week 12

Between-treatment differences in the change from baseline in SPARCC at Week 12 in the FAS will be compared by means of a MMRM with treatment regimen and analysis visit as factors and baseline weight and SPARCC score as continuous covariates. Study treatment by analysis visit will be included as an interaction term in the model. An unstructured covariance structure will be assumed for this model. The significance of the treatment effect for secukinumab at different analysis visits will be determined from the comparison to placebo.

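### SAP sections 2.6.2 and 5.5.2 give different fallbacks for the ACR 20/50 logistic model with no order of precedence, and the 2.6.2 version is faulty in itself; low impact, fixed by wording

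*SAP*

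**What the plan says.** Both sections start from the same model. SAP 2.6.2 has ACR 20 and ACR 50 at Week 12 "evaluated using a logistic regression model with study treatment as a factor and baseline weight as a covariate"; SAP 5.5.2 writes it as "ACR 20 at Week 12 = Treatment + weight" and adds "H_3 will be analysed analogous to H_2 above".

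They then differ on what happens if that model fails:

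- **SAP 2.6.2**, for ACR 20 and again for ACR 50: "In cases where separation is a concern for secondary endpoint at Week 12 an exact logistic regression model will be applied to all visits". Of the exact model it says "To ensure convergence, this model will not include any continuous covariates", and then "When exact logistic regression is unable to be implemented then Fisher's exact test will be applied". Of that last step it says "In this case no odds ratios or confidence intervals can be estimated but p-values may be calculated".
- **SAP 5.5.2**: "If the initial model does not converge Firth's penalized maximum likelihood estimation method will be used". Nothing there removes weight.

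SAP 2.8 analyses the exploratory binary outcomes of the double-blind period (ACR 20/50/70 and PASI 75/90/100 at the applicable visits) by analogy with the key secondary binary endpoints. It refers to section 2.6.2, not to 5.5.2.

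**The concern.** H2 and H3 belong to the alpha-controlled sequence in SAP 2.6.2, so each should have exactly one pre-specified analysis. The two triggers are worded differently (separation in one section, non-convergence in the other), but they overlap: separation is the usual cause of non-convergence in a two-term logistic model. One event can therefore invoke both rules. One leads to a weight-adjusted odds ratio; the other leads to an unadjusted one, or to none. With no precedence stated, the choice could be made after unblinding.

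The 2.6.2 rule also needs correction on its own terms, because SAP 2.8 carries it to tables where zero cells are more likely than at Week 12.

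**Working it through.** **Inputs.** 82 patients per arm (SAP 3.1). Week 12 placebo rates 29.6% (ACR 20) and 10.7% (ACR 50); secukinumab rates 63.5% and 33.3% (SAP 3.1, secondary variables). Family-wise error 5%, 1-sided (SAP 2.6.2). Patients who drop out count as non-responders (SAP 2.6.3), so the denominator stays at 82.

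**1. The plan's own figure.** SAP 3.1 states power above 90% for both endpoints. With the pooled-variance normal formula, power = Φ[(p1 − p0 − z·SE0)/SE1]:
- ACR 20: SE0 = 0.0779, SE1 = 0.0733; power 99.8% (1-sided 5%), 99.5% (2-sided 5%).
- ACR 50: SE0 = 0.0647, SE1 = 0.0622; power 97.3% and 94.5%.

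The figure reproduces. If Fisher's test without weight were used instead, exact enumeration at 1-sided 5% gives 99.6% and 96.2%, so the statement still holds.

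**2. The two rules side by side.**

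| | SAP 2.6.2 | SAP 5.5.2 |
|---|---|---|
| Trigger | separation a concern at Week 12 (no criterion given) | initial model does not converge |
| Method | exact logistic, then Fisher | Firth |
| Weight | dropped | not dropped |
| Visits changed | all | model stated for Week 12 |
| Odds ratio and interval | none at the Fisher step | odds ratio computed |

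**3. The exact model without weight.** Weight is the only covariate. Without it the model contains treatment alone, and its exact conditional distribution is the hypergeometric that Fisher's test uses. For 4/82 against 0/82 the 1-sided p-value is C(82,4)/C(164,4) = 0.060 under either name. The second step adds nothing.

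**4. Whether an interval exists.** It does. For 27/82 against 9/82 (close to the SAP's ACR 50 rates) the conditional odds ratio is 3.95, exact 95% CI 1.64 to 10.3. With a zero cell, 4/82 against 0/82, the conditional estimate is infinite, but the exact 95% interval is 0.67 to infinity: unbounded on one side, yet reportable.

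**5. How likely separation is at Week 12.** The realistic route is an arm with no responders. P(no placebo responder) = (1 − p)^82:
- ACR 20: 0.704^82 = 3e-13.
- ACR 50: 0.893^82 = 9e-5.

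**6. How likely it is elsewhere.** The SAP gives no early-visit or rare-response rates. For assumed placebo rates of 1%, 2%, 3% and 5%, the same formula gives 44%, 19%, 8% and 1.5%. PASI is scored only in patients with BSA of at least 3% (SAP 5.14), so its denominators may be below 82 and zero cells more likely still.

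**7. What the choice of method does when a zero cell occurs.** Treatment only, 82 per arm, 1-sided p. In this model Firth adds one half to each cell; for 4 v 0 the odds ratio is (4.5 × 82.5)/(0.5 × 78.5) = 9.46.
- Penalized likelihood ratio: 2 × [−16.140 − (−18.030)] = 3.78; √3.78 = 1.944; p = 0.026.
- Wald: SE = √[1/(82·p1(1−p1)) + 1/(82·p0(1−p0))] with p1 = 4.5/83 and p0 = 0.5/83, giving 1.508; z = ln(9.46)/1.508 = 1.490; p = 0.068.

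| Responders | Fisher | Firth, penalized LR | Firth, Wald |
|---|---|---|---|
| 3 v 0 | 0.123 | 0.054 | 0.097 |
| 4 v 0 | 0.060 | 0.026 | 0.068 |
| 5 v 0 | 0.029 | 0.012 | 0.050 |

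The spread within Firth is as large as the spread between Firth and Fisher. SAP 5.5.2 names neither the test nor the interval.

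**The case against.** The strongest reply is that nothing confirmatory depends on this, and for H2 and H3 that stands. At the SAP's rates, exactly 4/82 on secukinumab with 0/82 on placebo in ACR 50 has probability of about 4e-14. With no placebo responder and five or more on secukinumab, Fisher and the penalized likelihood ratio are both below 0.05.

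A reader might infer from 0.060 (Fisher) against 0.026 (Firth) that the two sections lead to opposite decisions. The SAP does not support that. The 0.026 needs a penalized likelihood-ratio test that the SAP never specifies; Firth with a Wald test gives 0.068, on the same side as Fisher. The comparison also leaves out weight, so it illustrates the model in 5.5.2 without reproducing it.

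A reader might also infer that rare responses such as ACR 70 or PASI 100 have no remedy at all. Applied by analogy, as SAP 2.8 says, separation in such an endpoint at its own Week 12 would trigger the exact model. Only separation confined to an earlier visit is left uncovered. SAP 2.8 also says that exploratory results are interpreted descriptively.

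Three further replies have some force. Exact methods are a legitimate pre-specified choice. A redundant Fisher step does no harm. One method for all visits keeps a table uniform. They do not answer the missing precedence, the incorrect statement about intervals, or the early visits that the trigger misses; and the uniformity is bought by removing weight from visits that have no separation.

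**Conclusion.** The point holds as a low-impact correction. SAP 2.6.2 and 5.5.2 prescribe different fallbacks, with different handling of weight and different reported estimates, for the same two alpha-controlled tests, and neither takes precedence. Within 2.6.2, the Fisher step duplicates the exact model, the statement that no interval can be estimated is wrong, and the trigger looks at Week 12 only while the remedy changes every visit.

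The effect on H2 and H3 is negligible: a zero placebo cell has probability 9e-5 (ACR 50) or 3e-13 (ACR 20), and power stays above 90% with either analysis. The practical effect is on early-visit and rare-response tables. There an uncorrected model can give an infinite odds ratio, or the table shows no estimate, although a finite weight-adjusted one is available from a method already in the SAP.

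This rests on the SAP's Week 12 rates, 82 independent patients per arm, and a zero cell as the main form of separation. The early-visit probabilities rest on assumed placebo rates of 1% to 5%.

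**What to change.** State one fallback, in the same words, in 2.6.2 and 5.5.2, and let 2.8 inherit it. Suggested content: if complete or quasi-complete separation is detected, or the model does not converge, for a given endpoint and visit, that endpoint and visit is analysed by Firth logistic regression with treatment and weight, reporting the odds ratio with a penalized profile-likelihood confidence interval and a 1-sided penalized likelihood-ratio p-value. Firth is the natural candidate because 5.5.2 already names it and it keeps the planned covariate.

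If the exact method is preferred, that is defensible too. In that case state that it takes precedence over Firth, remove the Fisher step and the statement about estimates, report the exact interval (unbounded on one side where a cell is zero), and apply the trigger by endpoint and visit.

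The cost is SAP wording only; sample size and data collection do not change. The one downside is that estimators may differ between visits within a table, which a footnote can flag.

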5.6 Rule of exclusion criteria of analysis sets

Table 7 Subject Classification

Analysis Set / Subgroup of interest	PD ID that cause subjects to be excluded	Non-PD criteria that cause subjects to be excluded
Randomized set	INCL01	Not randomized; Mistakenly randomized
FAS	INCL01	Not in RAN; Study treatment not assigned;

Analysis Set / Subgroup of interest	PD ID that cause subjects to be excluded	Non-PD criteria that cause subjects to be excluded
Safety set	INCL01	No study drug taken

5.7 Power Doppler Ultrasonography

Power Doppler and Grayscale ultrasound (PDUS) is a non-invasive imaging method to assess peripheral involvement of SpA, including PsA. This technique permits visualization of most of the relevant joint pathologies associated with SpA, including synovitis, bone erosions, peripheral enthesitis, bursitis, tenosynovitis [11].

The Outcome Measures in Rheumatology and the European League Against Rheumatism (OMERACT-EULAR) Ultrasound Task Force has developed a composite scoring system (the OMERACT-EULAR global synovitis score (GLOESS) as measured using PDUS) to detect and score synovitis at patient level. This score combines Grayscale-assessed synovial hyperplasia with an intra-synovial Power Doppler signal for evaluating synovial activity at joint level.

PDUS evaluation will be performed at each joint site out of 48. The PDUS will be performed bilaterally for 24 pairs of joints:

- Metacarpophalangeal (MCP) joints 1 to 5.
- Proximal interphalangeal (PIP) joints 1 to 5.
- Metatarsophalangeal (MTP) joints 1 to 5.
- Wrist, elbow, shoulder (glenohumeral), knee, and ankle (tibiotalar).
- Distal interphalangeal (DIP) 2 to 5.

The PDUS assessment will consist of an evaluation of hypoechoic synovial hyperplasia (SH) and joint effusion (JE) using Grayscale and synovial vascularization using Power Doppler. The pre-specified set of 24 paired joints will be scanned at each visit from the dorsal aspect with the joint in a neutral position, except for the knee, which will also be examined in a flexed position (30°). Note: only affected joints will be assessed after Visit 2 (Baseline). Standardized joint and probe positions will be used based on a reference atlas, which also show examples of synovitis grading for each site examined. The presence of synovitis (i.e. SH and Power Doppler, without JE) will be scored according to the OMERACT-EULAR PDUS composite semi-quantitative scale (0 to 3).

For the enthesis evaluation, ultrasound will be initially performed in B mode to detect morphologic abnormalities, and subsequently with power Doppler to detect abnormal vascularization at bony insertions. The following entheses will be examined bilaterally:

1. Common extensor tendon at its insertion at the lateral humeral epicondyle.
2. Quadriceps tendon at its insertion at the superior pole of the patella.

3. Patellar tendon at its proximal insertion at the inferior pole of the patella.
4. Patellar tendon at its distal insertion at the tibia tuberosity.
5. Calcaneal insertions:
 - a. Achilles tendon at its insertion at the calcaneus.
 - b. Plantar aponeuroses at its insertion at the calcaneus.

Each affected enthesis out of 6 targeted entheses will be scored in terms of inflammatory and morphological components according to the OMERACT enthesitis composite semi-quantitative scale (0 to 3).

5.8 The classification criteria for psoriatic arthritis (CASPAR)

To meet the classification criteria for psoriatic arthritis (CASPAR) for diagnosis of psoriatic arthritis according to ([Taylor 2006](#)) a patient must have inflammatory articular disease (joint, spine or enthesal) and at least 3 points from the following 5 categories:

1. Evidence of current psoriasis, a personal history of psoriasis, or a family history of psoriasis
 - Current psoriasis is defined as psoriatic skin or scalp disease present today as judged by a rheumatologist or dermatologist* (**2 points**).
 - A personal history of psoriasis is defined as a history of psoriasis that may be obtained from a patient, family physician, dermatologist, rheumatologist, or other qualified health care provider (**1 point**).
 - A family history of psoriasis is defined as a history of psoriasis in a first- or second- degree relative according to patient report (**1 point**).
2. Typical psoriatic nail dystrophy including onycholysis, pitting, and hyperkeratosis observed on current physical examination (**1 point**).
3. A negative test result for the presence of rheumatoid factor by any method except latex (**1 point**).
4. Either current dactylitis, defined as swelling of an entire digit, or a history of dactylitis recorded by a rheumatologist (**1 point**).
5. Radiographic evidence of juxta-articular new bone formation appearing as ill-defined ossification near joint margins (but excluding osteophyte formation) on plain radiographs of the hand or foot (**1 point**).

Total score: If the total score is ≥ 3 , the patient meets the CASPAR criteria for psoriatic arthritis diagnosis.

* Current psoriasis is assigned a score of 2; all other features are assigned a score of 1.

5.9 American College of Rheumatology measures and criteria of response

The ACR has seven criteria:-

Number of tender joints:

The 78 joints assessed for tenderness include the 2 temporomandibular, 2 sternoclavicular, 2 acromioclavicular joints, 2 shoulders, 2 elbows, 2 wrists, 2 first carpometacarpal, 10 MCP, 10 PIP, 8 distal interphalangeal joints of the hands, the 2 hip, 2 knee, 2 talo-tibial, 2 mid-tarsal, 10 MTP, 10 PIP, and 8 DIP joints of the feet.

Joint tenderness and swelling are to be graded present (1) or absent (0).

Number of swollen joints:

Joints are to be scored as either swollen (1) or not swollen (0). The 76 joints to be examined for swelling are the same as those examined for tenderness, however excluding both hip joints.

Patient's assessment of psoriatic arthritis pain

The patient's assessment of pain will be performed using 100 mm VAS ranging from "no pain" to "unbearable pain" after the question "Please indicate with a vertical mark (|) through the horizontal line the most pain you had from your PsA today".

Patient's global assessment of disease activity

The patient's global assessment of disease activity will be performed using 100 mm VAS ranging from "very good" to "very poor", after the question "Considering all the ways PsA affects you, please indicate with a vertical mark (|) through the horizontal line how well you are doing today".

Physician's global assessment of disease activity

The PGA of disease activity will be performed using 100 mm VAS ranging from no disease activity to maximal disease activity, after the question "Considering all the ways the disease affects your patient, draw a line on the scale for how well his or her condition is today." To enhance objectivity, the physician must not be aware of the specific patient's global assessment of disease activity when performing his own assessment on that patient.

High sensitivity C-reactive protein

The purpose of this assessment is to identify the presence of inflammation, to determine its severity, and to monitor response to treatment. As the results of this test may unblind study personnel (such as the Ultrasonography Investigator and Clinical Investigator), results from the central laboratory will be provided for Screening and Baseline only. The hsCRP results from samples collected during the treatment period will be revealed following database lock only.

Patient's assessment of physical function

Health Assessment Questionnaire – HAQ-DI[©] (reference Appendix 5.13)

5.10 OMERACT-EULAR Global PDUS OMERACT out of 48 joints

The Outcome Measures in Rheumatology-Ultrasound (OMERACT-US) Task Force, with funding received from the European League Against Rheumatism (EULAR), works to standardize the use of ultrasonography in rheumatoid arthritis (RA) and has developed a composite scoring system (the OMERACT-EULAR composite PDUS score) to detect and score synovitis. This score combines Greyscale-assessed synovial hyperplasia with an intra-synovial power Doppler signal for evaluating synovial activity. The score has demonstrated validity and intra- and inter-observer reliability in cross-sectional datasets, applicability to all joints and consistency between machines

The PDUS assessment will consist of an evaluation of hypoechoic synovial hyperplasia (SH) and joint effusion (JE) using Greyscale and of synovial vascularization using Power Doppler. The pre-specified set of 24 paired joints will be scanned at each visit on the dorsal aspect, with the joint in a neutral position, except for the knee, which will also be examined in a flexed position (30°). Standardized joint and probe positions will be used, based on a reference atlas, which also shows examples of synovitis grading for each site examined.

The presence of synovitis (i.e. SH and Power Doppler, without JE) will be scored according to the OMERACT-EULAR PDUS composite semi-quantitative scale (0 to 3; Table 8).

Each single component of joint inflammation (SH, Power Doppler, JE) was also scored separately at each visit, using semi-quantitative scales (0 to 3; Table 8). The global PDUS scores for the 24 paired joints will then be calculated using the sum of the composite PDUS scores for all joints examined, giving a potential score and of 0 to 144 for the 24 paired joints.

Table 8: Ultrasound scoring system

Greyscale ultrasound	
Joint effusion	
Grade 0	No effusion
Grade 1	Minimal amount of joint effusion
Grade 2	Moderate amount of joint effusion (little distension of the joint capsule)
Grade 3	Extensive amount of joint effusion (with high distension of the joint capsule)
Inflammatory or active synovial hyperplasia (hypoechoic)	
Grade 0	No hypoechoic synovial thickening
Grade 1	Minimal hypoechoic synovial thickening (filling the angle between the periarticular bones, without bulging over the line linking tops of the bones)
Grade 2	Hypoechoic synovial thickening bulging over the line linking tops of the periarticular bones but without extension along the bone diaphysis
Grade 3	Hypoechoic synovial thickening bulging over the line linking tops of the periarticular bones and with extension to at least one of the bone diaphysis

Power Doppler signal	
Grade 0	No flow in the synovium
Grade 1	Up to 3 single spots signals or up to 2 confluent spots or 1 confluent spot plus up to 2 single spots
Grade 2	Vessel signals in less than half of the area of the synovium (< 50%)
Grade 3	Vessel signals in more than half of the area of the synovium (> 50%)
OMERACT-EULAR composite PDUS score (for individual joints)	
Grade 0 (normal joint)	No greyscale-detected synovial hyperplasia or Power Doppler signal i.e. B MODE=0 and Doppler=0
Grade 1 (minimal synovitis)	Minimal synovial hyperplasia and ≤ Grade 1 Power Doppler signal i.e. B MODE=1 and Doppler ≤1 OR B MODE=0 and Doppler=1 For revised GLOESS : Minimal synovial hyperplasia and ≤ Grade 1 Power Doppler signal i.e. B MODE=1 and Doppler ≤1
Grade 2 (moderate synovitis)	Moderate synovial hyperplasia and ≤ Grade 2 Power Doppler signal or minimal synovial hyperplasia and a Grade 2 Power Doppler signal i.e. B MODE=2 and Doppler ≤2 or B MODE≤2 and Doppler=2
Grade 3 (severe synovitis)	Severe synovial hyperplasia and ≤ Grade 3 Power Doppler signal or moderate synovial hyperplasia and a Grade 3 Power Doppler signal i.e. B MODE=3 and Doppler ≤3 or B MODE≤3 and Doppler=3
Global OMERACT-EULAR synovitis score (GLOESS)	Sum of composite PDUS scores for all joints assessed (e.g. for MCPs 2–5, Global PDUS score would range from 0 to 24)

Note: B MODE is hypoechoic synovial hypertrophy independently of the presence of effusion.

The revised GLOESS definition will also be known as GLOESS definition 2 with the original GLOESS derivation known as GLOESS definition 1.

Proportion of patients with a presence of PDUS synovitis (Composite PDUS, SH and PD) will be summarised over time.

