2.5.4 Supportive analyses

Sensitivity analyses and supportive analyses will be conducted in order to provide evidence that the results seen from the primary analysis are robust. These analyses will center on the deviations in model assumptions, the treatment of missing data and protocol deviations/audit findings.

[REDACTED]

[REDACTED]

[REDACTED]

[REDACTED]

[REDACTED]

[REDACTED]

[REDACTED]

[REDACTED]

[REDACTED]

The GLOESS score will be revised to account for a small number of composite PDUS scores that are not in agreement with the definition of synovitis that power doppler alone does not mean synovitis ([D'Agostino \(2016\)](#), [Terslev L \(2016\)](#)). This endpoint will be named 'GLOESS revised (Definition 2).' and the primary analysis (MMRM) will be repeated on the revised definition.

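### The revised GLOESS (Definition 2) is meant to stop Doppler-only joints counting as synovitis, but Table 8 drops only the mildest such joints, still scores the others 2 or 3, and leaves B-mode 0 with Doppler 1 ungraded.

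*SAP*

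**What the plan says.** Section 2.5.4 gives the reason for a second version of the primary score: a small number of composite joint scores are "not in agreement with the definition of synovitis that power doppler alone does not mean synovitis". It then commits that "the primary analysis (MMRM) will be repeated on the revised definition". Section 5.10 names the revised score Definition 2 and the original Definition 1.

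Table 8 in section 5.10 holds the joint-level rules:

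- Grade 0, one version only: "No greyscale-detected synovial hyperplasia or Power Doppler signal i.e. B MODE=0 and Doppler=0".
- Grade 1, Definition 1: "i.e. B MODE=1 and Doppler ≤1 OR B MODE=0 and Doppler=1". A second entry, beginning "For revised GLOESS : Minimal synovial hyperplasia", keeps only the B-mode 1 part.
- Grade 2, one version only: "i.e. B MODE=2 and Doppler ≤2 or B MODE≤2 and Doppler=2".
- Grade 3, one version only: "i.e. B MODE=3 and Doppler ≤3 or B MODE≤3 and Doppler=3".

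GLOESS is the sum of these grades over the joints. Section 4 states that the composite rules were refined so that every permutation of the component data is covered.

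**The concern.** The principle in section 2.5.4 concerns joints with Doppler signal and no hyperplasia, that is, B-mode 0 with Doppler 1, 2 or 3. Table 8 acts on the first of these and is silent on the other two. Because the Grade 2 and Grade 3 formulas use upper bounds on B-mode (at most 2, at most 3), they take in B-mode 0. The same absence of hyperplasia thus disqualifies a joint at Doppler 1 but leaves it as moderate or severe synovitis at Doppler 2 or 3.

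The joint that was removed has nowhere to go. Grade 0 still requires Doppler 0, and no revised Grade 0 rule exists. One programmer may set it to 0; another may leave it missing, with or without making the patient's visit total missing.

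What is at stake is the claim the supportive analysis would support. A report could say that the primary result is robust to removing Doppler-only joints when the highest-scoring of them had been kept.

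**Working it through.** **Inputs.** B-mode (synovial hyperplasia) and Doppler are each graded 0 to 3 (section 5.10), which gives 4 × 4 = 16 combinations. The grade rules are the formulas of Table 8. The purpose of Definition 2 is in section 2.5.4.

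**The plan's own figure.** 48 joints × maximum grade 3 = 144, which matches the 0 to 144 range in section 5.10.

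**Step 1: grade every combination.** Rows with B-mode 1, 2 or 3 (12 cells) have exactly one grade each and are the same under both definitions. Definition 1 equals the larger of the B-mode and Doppler grades in all 16 cells. The B-mode 0 row is where the definitions part:

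| B-mode 0 with | Doppler 0 | Doppler 1 | Doppler 2 | Doppler 3 |
|---|---|---|---|---|
| Definition 1 | 0 | 1 | 2 | 3 |
| Definition 2 as written | 0 | none | 2 | 3 |
| Definition 2 by the stated principle | 0 | 0 | 0 | 0 |

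As written, Definition 2 grades 15 of 16 cells and differs from Definition 1 in one. Of the three Doppler-only cells, the 1-point cell is dropped without a replacement grade, and the 2-point and 3-point cells remain.

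**Step 2: effect on change from baseline.** Take a joint with B-mode 0 throughout, and read the ungraded cell in the most favourable way, as 0:

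| Doppler moves | Definition 1 | Definition 2 as written | By the principle |
|---|---|---|---|
| 1 to 0 | −1 | 0 | 0 |
| 2 to 1 | 2 to 1 = −1 | 2 to 0 = −2 | 0 |
| 3 to 1 | 3 to 1 = −2 | 3 to 0 = −3 | 0 |
| 2 to 0 | −2 | −2 | 0 |
| 3 to 0 | −3 | −3 | 0 |

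Even on that reading, two of these five Doppler-only moves count for more under the revised score than under the original, and two count the same. If the ungraded cell is set to missing, the moves that end at Doppler 1 have no defined change.

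**Step 3: words against formulas.** In words, the Grade 2 row pairs Doppler 2 with minimal or moderate hyperplasia, and the Grade 3 row pairs Doppler 3 with moderate or severe hyperplasia. Neither mentions absent hyperplasia. Following the words alone would leave B-mode 0 with Doppler 2, B-mode 0 with Doppler 3, and also B-mode 1 with Doppler 3 without a grade. The words therefore do not rescue Definition 2. They disagree with the formulas.

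**Step 4: scale.** With 82 patients per arm, a shift of 1 point in a simple arm mean needs a net 82 points. That is 82 / 2 = 41 joints at B-mode 0 and Doppler 2 resolving fully, out of 82 × 48 = 3,936 joint positions. The SAP gives no cell counts, so whether anything of that order occurs is unknown.

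**The case against.** The strongest reply is that little depends on this. The primary endpoint uses Definition 1, whose formulas grade every combination once. Definition 2 feeds a repeat MMRM outside the H1 to H4 testing sequence, so no error rate, power figure or confirmatory conclusion changes. That stands, and it limits the weight of the point.

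Second, the SAP expects only a small number of affected scores, and Doppler grades 2 and 3 may be uncommon where no thickening is seen. This is plausible, but the document does not show it or confine the affected scores to Doppler 1. It is equally true that nothing shows these cells to be frequent.

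Third, the ungraded joint is most likely meant to be Grade 0, and a joint left out of a sum contributes 0 anyway. The intention is probably right, but the Grade 0 row excludes that joint and section 4 says every permutation is covered. Granting Grade 0 does nothing for the Doppler 2 and 3 cells and, as Step 2 shows, can enlarge a Doppler-only change.

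Fourth, 2 or 3 points in one joint of one patient should not be read against the planned group-mean difference of 3.5 to 4.352. That is correct: a joint with the same grade at both visits adds nothing to change, and a bias needs such joints to change differently between arms. The per-joint figures show what the rule leaves in, not the size of any bias.

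Fifth, the formulas may be read as the declared refinement of the shorter verbal text, which makes aligning the Definition 1 wording an editorial matter. That is fair.

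**Conclusion.** The point holds. Section 2.5.4 and Table 8 contradict each other: followed as written, Definition 2 removes one of three Doppler-only cells, keeps the other two at 2 and 3 points per joint, and leaves the removed one without a grade. The repeat MMRM is thus an incomplete check of the question it was set up to answer, and its result would depend in part on a programmer's choice for the ungraded cell.

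The reach is limited to that supportive analysis; the primary analysis is unaffected. The conclusion rests on reading the Table 8 formulas literally and on taking the rationale in section 2.5.4 to apply at every Doppler grade. The effect on the estimated treatment difference cannot be stated without the frequencies of the B-mode 0 cells by visit and arm. This should be corrected, but it does not threaten the confirmatory result.

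**What to change.** Give Definition 2 its own complete set of rules in Table 8:

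- Grade 0: any joint with B-mode 0, whatever the Doppler grade.
- Grade 1: B-mode 1 and Doppler at most 1.
- Grade 2: B-mode 2 and Doppler at most 2, or B-mode 1 and Doppler 2.
- Grade 3: B-mode 3 with any Doppler grade, or B-mode 1 or 2 with Doppler 3.

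This gives each of the 16 combinations exactly one grade (4 cells in each B-mode row), sets all three Doppler-only cells to 0, and leaves the other 12 cells and the 0 to 144 range unchanged. In short, the grade is 0 if B-mode is 0, and otherwise the larger of the two component grades.

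Keep Definition 1 for the primary analysis, and align the verbal text of its Grade 2 and Grade 3 rows with its formulas. A count of B-mode 0 joints by Doppler grade, visit and arm beside the repeat MMRM would let a reader see how much the revision can matter.

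The cost is a few lines of SAP text and one derivation program. The component grades are already scored separately at each visit, so no new data are needed.
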